The primary process outcomes are the number and proportion of smokers that can be recruited for further follow-up, including those who will not participate in the RCT but agree to enroll in the SC clinics. We hypothesize that the promotion sessions providing NRT sampling will recruit more smokers, and greater proportion of recruited smokers among those who will be approached than those sessions without NRT sample. Other secondary process outcomes include (1) total number of smokers who can be approached in outdoor urban places; and (2) number of smokers who accept the brief SC advice. All these indicators will be documented by the SCAs in the promotion sessions.

Phase 3: Quitting outcomes

The evaluation aims to assess the effectiveness of NRT sampling on using the SC services and quit attempts, by comparing the outcomes between the experimental group and the control group. The two primary outcomes include (1) the proportion of smokers who enroll in any SC service in Hong Kong within 1 month of the recruitment; and (2) the proportion of smokers who report quit attempts at 1 month follow-up. Secondary outcomes include (1) the above outcomes at 3-month follow-up; (2) self-reported use of NRT in past month at 1- and 3-month follow-up; (3) self-reported tobacco abstinence in past 7 days and 4 weeks at 3- and 6-month follow-up; (4) biochemically validated abstinence at 6-month follow-up; (5) perceived importance, difficulty and confidence to quit smoking (score 0-10); (6) progression towards smoking cessation as measured by Incremental Behavior Change toward Smoking cessation (IBC-S) [1]. All self-reported outcomes will be assessed either

by telephone or WhatsApp by allocation-blinded interviewers at 1, 3 and 6 months after the recruitment. Self-reported quitters (no use of tobacco products for 7 days) will be invited for examination of exhaled carbon monoxide with a Smokerlyzer, and to undertake a saliva cotinine test. Validated quitters were defined by exhaled CO < 4 ppm and salivary cotinine < 10 ng/ml, which have been confirmed as the cut-off in clinical trials to verify smoking abstinence [2,3]. A HK\$50 shopping voucher will be given for each participation of follow-up and biochemical validation. We have much experience for the above and have reported these in many papers [4-8].

6. Estimated duration and commencement date

Proposed starting date: 1 July 2018

Proposed study completion date: 30 June 2020

Expected final report date: 30 June 2020

7. Scientific/historical background

Health needs of the local community

Smoking causes cancers, coronary heart diseases and many more chronic diseases. Hong Kong still has more than 640 thousands daily smokers [9], and half of them will die of smoking-related diseases [10]. Although free smoking cessation (SC) services and occasional promotion activities are available, about 30.8% of daily cigarette smokers in Hong Kong have tried but failed to quit smoking, and 63% have never tried and did not want to quit [9]. The existing SC services have difficulties to attract smokers to come forward, but service providers lack resources and cost-effective methods to recruit smokers proactively. More specific interventions to enhance the utilization of SC service and quit attempts are needed.

Very few healthcare professionals can deliver SC counselling or other interventions in the busy clinical settings [11-13]. To promote SC in the community, brief SC advice (AWARD, See Implementation plan/Procedure) and training of non-healthcare professionals for delivery of simple SC advice have been well developed by our team in Hong Kong [5, 7]. Yet, the recruitment for smokers is still difficult as we have shown that “hardcore” smokers – who are less motivated to quit and less likely to seek service – are increasing in Hong Kong [14]. Also, more immediate quitting assistance is needed for the recruited smokers in

the community-based SC promotion [6, 15], as any delay can result in default.

Smokers are addicted to tobacco because tobacco delivers nicotine to the central nervous system, which leads to the desired psychological reactions and induces dependence. In the early phase of quitting, the lack of nicotine causes withdrawal symptoms such as headache, coughing, difficulty in concentration etc. By slowly delivering nicotine to cope with the dependence, nicotine replacement therapy (NRT) is a safe and effective pharmacotherapy to reduce withdrawal symptoms during early abstinence and smoking reduction, which increases the quit rate by 4-fold in the longer term [16]. A recent study has shown that NRT works better than many other behavioral interventions for smoking cessation [17]. Although NRT can be purchased over the counter without doctor's prescription, or obtained freely from local SC clinics, only 9.8% of quit attempters had used medications for their quit attempts [9]. The corresponding proportion in Australia, Canada, the UK and the USA is at least 30% [18, 19]. In contrast, over 80% of Hong Kong quit attempters relied on self-determination [9], which has a low success rate and easily leads to smoking relapse. The low prevalence of using NRT may be due to the higher absolute price of NRT per day (US\$5.43 per day) [8] than, say, in the USA (US\$2.41–3.62 per day) [20], and the low utilization of SC services which provide free NRT.

Although some social marketing of SC has been done in Hong Kong, very few programmes promote the use of NRT. Existing SC services provide free NRT to smokers, but the smokers must first enroll in the SC services. That means majority of smokers, who do not know or use SC services, have low literacy of NRT use and its effectiveness.

To sum up, the following health care needs regarding SC promotion in Hong Kong should be addressed: (1) Many current smokers still have no quitting intention (2) Many smokers are unable to quit smoking using self-determination, (3) The low success rate of quitting is attributed to the under-utilization of existing SC service and low use of effective medications such as NRT.

Literature review on others' strategies to address these needs

Proactive approach of smokers at outdoor smoking hotspots is a new strategy initiated by our team to promote smoking cessation. Smoking hotspots are non-smoke-free urban places where many smokers gather to smoke around a rubbish bin with an ash tray to collect cigarette butts. We applied this approach by training university students to deliver brief SC

intervention to the smokers at these hotspots [15]. The brief intervention included brief advice, printed materials and introduction of the quitline ([name]). This pilot study showed that this approach was feasible and accepted by the smokers [15].

To further show the efficacy and cost for this approach, we obtained funding from the Health Care and Promotion Fund to extend the promotion and evaluate more outcomes in 2014-15 (Ref no. 06130205). This funded project showed that the promotion approached 3096 smokers and recruited 210 smokers at a reasonable cost, particularly for youth smokers and those who wanted to quit [6]. About 10% of the recruited smokers from smoking hotspots reported abstinence at 6-month follow-up. Upon the invitation of the Health Research Symposium 2017, we presented a paper about this study on 16 June 2017. The findings of this study has been published in a renowned tobacco and public health journal (Nicotine and Tobacco Research)[6].

Further developments and improvements are needed to increase the impacts. First, the recruited smokers in the community were not further given more tailored and intensive interventions, and therefore some particularly heavy-smoking smokers would feel difficult to quit. We found that about 72% of the recruited smokers had intention to quit, who should be receptive for further intervention. Second, majority of the approached smokers did not consent to the follow-up by counsellors. These smokers, who were similar to the majority of smokers in the community, probably chose to quit without seeking assistance from healthcare professionals [7], or were hardcore smokers who were less likely to notice or use available SC services [14].

These service gaps could be filled by (1) designing more effective ways to motivate quitting intention, (2) providing more immediate information and motivation of using NRT in their quit attempts, (3) enhancing smokers to try NRT first, (4) enhancing the continuing access of NRT through enrolling in the SC services or purchasing NRT over-the-counter.

Scientific evidence supporting the strategies to address these needs proposed in this project

Providing NRT sample and brief advice to the non-help-seeking smokers who are recruited at smoking hotspots is novel and warrants further exploration. Receiving free NRT immediately after recruitment can reduce the financial and time cost for trying this effective medicine. Previous randomized trials have confirmed that the delivery of NRT sample (less than 5-week dosage) increased quit attempts and prolonged abstinence [21-23]. The NRT

sample also increased smokers' motivation and confidence to quit [21, 22]. The smokers in these trials were recruited in the community, and they were either unmotivated to quit, or not ready to receive intensive smoking cessation. No or only brief counselling sessions were included in these interventions. Therefore, delivering NRT sample immediately after giving SC advice to the smokers may increase the motivation to quit and use of quitting assistance. Also, the findings from the studies above are particularly applicable to our SC promotion in smoking hotspots which targets similar smokers in the community.

The feasibility and effectiveness of providing NRT sample at smoking hotspots is novel and has been preliminarily evaluated by our team. We propose 1-week NRT as it is the cheapest and has been shown that the effectiveness on abstinence was similar to 2-week NRT [24]. In a feasibility study conducted by the SC clinics of Tung Wah Group of Hospitals (TWGHs), about three quarters of the approached smokers at outdoor smoking hotspots (77.6%, 548/706) accepted NRT sample. In the smokers who received the NRT sample, about 40.1% (n=220) enrolled in the SC service. In our recent pilot randomized controlled trial (RCT), we examined if 1-week NRT could improve quitting outcomes in the smokers who were recruited at smoking hotspots. The study protocol has been published in the journal Trials [25]. In all the invited smokers in the recruitment, the proportion of participation was very high (81.3%). The preliminary results showed that NRT sampling substantially increased use of NRT (34% versus 2%, Risk ratio = 17.00, 95% CI 2.33-124.15) and quit attempt (defined as no smoking intentionally for at least 24 hours, 26% versus 12%, RR = 2.17, 95% CI 0.89-5.27) at 3-month follow-up. These findings have shown that using NRT sample to enhance quitting and using SC services is feasible and well accepted. However, due to the small sample size and wide confidence intervals of the trial results, the results hardly confirmed the effectiveness for the quitting outcomes. Also, the pilot study had not provided additional medication and other support, and had not referred the smokers to SC clinics, hence the 6-month quit rate was low (about 8%).

8. Study design

The proposed project has 4 phases: (1) Training of SC ambassadors (SCAs) for the SC promotion; (2) SC promotion sessions to deliver the medication counselling and NRT sampling (experimental group), or the advice to use NRT only (control group); (3) Follow-up of the recruited smokers; (4) Evaluation of the effectiveness of training, promotions, and use of NRT sampling. To examine the effectiveness of NRT sampling for recruitment and

quitting, a multi-site cluster RCT (allocation ratio 2:1) will be used. All promotion sessions will be randomly allocated to either the experimental or the control group. The experimental group will receive medication counselling and NRT samples, while the control group only receive the advice to use NRT. Because smokers who receive NRT sampling will be more likely to participate in the study, the experimental sessions will then recruit more smokers than the control sessions. Hence, the allocation ratio of participants is arbitrarily set at 2:1. To increase comparability between the two groups, the promotion sessions of one hotspot will be randomly allocated to either group. All recruitment and quitting outcomes in the smokers between the experimental and control group will be compared.

9. Subjects

Smokers with the following inclusion criteria will be invited to participate in our RCT: (1) Hong Kong residents, (2) aged 18 to 65 years, (3) have used any tobacco products in the past month, (4) able to read and speak Chinese, (5) have not used NRT for the past month, (6) no severe angina, serious cardiac arrhythmias and hypertension, (7) have not suffered acute myocardial event in the past 4 weeks, (8) neither pregnant nor breastfeeding, (9) not under medication and treatment due to mental illness. To confirm the smoking status, in those who use conventional cigarettes, smokers' exhaled carbon monoxide will be measured on-site. Nurses on truck will measure the blood pressure if smoker is aged over 50 years old, obese by observation, or upon patient requests.

10. Procedures

In the experimental sessions, the SCAs will approach and distribute souvenirs (e.g. a pen) or leaflets to the smokers at outdoor smoking hotspots for 3-4 hours. The souvenirs and leaflets will have SC messages, quitline number and other SC services. If a smoker is willing to accept them and talk to the SCAs, the SCAs will advise the smoker to quit using the AWARD protocol. The AWARD protocol includes (1) Ask the smoking history, (2) Warn about the high risk (i.e., half of the smokers will die of smoking-related diseases), (3) Advise to quit, (4) Refer to the SC clinics of TWGHs and (5) Repeat the above advice (Do-it-again) [4]. Our previous studies have shown that the AWARD protocol is a feasible and appropriate tool used by non-healthcare professionals to promote smoking cessation [4-6]. If the smoker is interested in using the SC services, the SCAs will introduce NRT to the smoker and conduct a preliminary assessment of his/her eligibility for enrolling in the "NRT sampling" programme. The SCAs will invite him/her to go to the smoking cessation

truck nearby to receive counselling by an onsite nurse. If the smoker is not eligible, he/she can still enroll in the cessation service provided by the SC clinics.

11. Intervention: NRT sampling and medication counselling

In the experimental sessions, an onsite nurse will assess whether each participant is fit for using NRT with further assessment on his/her current physical status, medication and blood pressure. If the participant is willing to use NRT to quit smoking and pass the nurse's assessment, he/she will be prescribed the NRT sample, regardless of whether they use NRT for smoking reduction and when the quit day is. The nurse will help the participant decide which type of NRT product (gum: 2mg, patch: 14mg or 21mg) that he/she can use and advise him/her on how to use the NRT based on his/her smoking habit and daily cigarette consumption. In addition, the nurse will deliver medication counselling which addresses five main components: (1) the benefits for using NRT in quitting, (2) withdrawal symptoms due to smoking cessation, (3) side effects of NRT, (4) instructions for using NRT, and (5) making appointments for TWGHs SC clinics. Afterwards, the participant will receive 1-week free NRT and an instruction card about the use of NRT.

In the control sessions, all the above procedures for the experimental group will be applied, except that they will not receive an NRT sample and an instruction card about the use of NRT. Instead, they will be advised to obtain free NRT by enrolling in the SC clinics. Both groups will receive a one-page leaflet provided by the SC clinics.

As this trial is a pragmatic trial, flexible procedures will be adopted based on the actual interaction with the participant. Firstly, the intervention components and filling in of baseline questionnaire may be carried out prior to seeking the consent from the participant if it is deemed more suitable in the situation and can make the procedures run more smoothly. Secondly, if the recruitment venue is not suitable for drug dispensing, the NRT sample and the use instructions will be register-mailed to the participants' address instead of given immediately. All NRT will be prescribed by registered nurses. The research assistant will also contact the participants to confirm that they have received the NRT. This arrangement of mailing the NRT sample complies with the Pharmacy and Poisons Ordinance of the Drug Office.

12. Randomization

We will use cluster randomization based on promotion session as the cluster unit because the procedures of individual randomization are difficult in outdoor areas as found in our pilot RCT. The PI will randomly allocate the promotion sessions within a hotspot to the 2 groups by a list of group allocation which is based on a list of random numbers from Excel programme. Each hotspot will have 2 or more promotion sessions, and each session will last for about 3-4 hours. If a hotspot has 2 promotion sessions on 1 single day, the 2 sessions will be allocated into the same RCT group, and we will organize 2 more promotion sessions in this hotspot on another day.

13. Allocation concealment

All recruitment staff will know the group allocation before each promotion session, so no group concealment can be done.

14. Blinding

Participants cannot and will not be blinded to the intervention. Assessors of the follow-up outcomes and the research analysts will not be involved in the recruitment and intervention delivery, and will be blinded to the group allocation (single blindness).

15. Follow-up

All the smokers who consent to the follow-up will be contacted via telephone or WhatsApp around one week by a nurse or a research assistant after recruitment. The aim of this follow-up is to enquire if there is any progress towards cessation and encourage the use of NRT and/or enrollment in SC services.

At 1-, 3- and 6-month follow-up, the quitting outcomes will be assessed by a trained interviewer through telephone who is blinded to the subject's group status.

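### Validated 6-month abstinence requires low salivary cotinine with no provision for current NRT users, so this secondary outcome could be understated by an amount the documents do not give (minor)

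*Combined protocol and SAP*

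**What the plan says.** Section 5 (Phase 3) makes biochemically validated abstinence at 6 months a secondary outcome. Entry to testing depends on tobacco use: "Self-reported quitters (no use of tobacco products for 7 days) will be invited for examination of exhaled carbon monoxide with a Smokerlyzer", together with a saliva cotinine test. Both markers must then be passed: "Validated quitters were defined by exhaled CO < 4 ppm and salivary cotinine < 10 ng/ml". No section contains an exception, a CO-only rule, another marker or a sensitivity analysis for people using NRT when tested.

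The same section lists NRT use as an outcome in these terms: "self-reported use of NRT in past month at 1- and 3-month follow-up". It also says that the self-reported outcomes are all assessed at 1, 3 and 6 months.

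On exposure to NRT:

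- Section 7 describes it as a nicotine product: "By slowly delivering nicotine to cope with the dependence, nicotine replacement therapy (NRT) is a safe and effective pharmacotherapy".
- Section 11 gives eligible experimental participants a short supply: "the participant will receive 1-week free NRT and an instruction card about the use of NRT".
- Section 11 has control participants advised to get free NRT through the cessation clinics.
- Section 15.1.1.1 has experimental participants who have used NRT encouraged to obtain more from the clinics or, if unwilling to enroll, advised to buy it.

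On tobacco products, the Section 9 entry criterion is broad: "have used any tobacco products in the past month". On-site CO measurement at entry is limited to some of those people: "in those who use conventional cigarettes".

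**The concern.** The entry condition and the validation rule measure different things. The first asks about tobacco. The second, through cotinine, also picks up nicotine that did not come from tobacco. A participant who has stopped all tobacco but regularly uses NRT at the 6-month test satisfies the first and would be expected to fail the second, and would then be counted with those whose claim of abstinence was not confirmed.

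The trial promotes NRT and directs both arms to more of it, so this can occur in either arm. At stake are the absolute validated abstinence rate and possibly the between-arm comparison on that outcome. The plan also does not commit to reporting how many people fail on cotinine alone, or to using NRT status when validating. Readers may therefore be unable to separate likely misreporting from continued NRT use.

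**Working it through.** The documents state no expected rate or power for validated abstinence, so there is no figure for this outcome to reproduce. The Section 16 targets give a base case.

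**Inputs (Section 16).** Cessation-service users: 288 of 720 experimental and 72 of 360 control. Self-reported 6-month abstainers: 108, given as 30% of the 360 service users in both groups combined.

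**Step 1: reproduce the target.** 0.30 × (288 + 72) = 0.30 × 360 = 108, as stated.

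**Step 2: split by arm.** The plan gives only the pooled figure. Assume that the 30% applies in each arm and that nobody outside the services abstains:

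- Experimental: 0.30 × 288 = 86.4; 86.4/720 = 12.0%.
- Control: 0.30 × 72 = 21.6; 21.6/360 = 6.0%.
- Difference 6.0 points; risk ratio 12.0/6.0 = 2.00.

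**Step 3: apply the rule.** Let uE and uC be the shares of abstainers on NRT at the test. Assume that every self-reported abstainer is tobacco-free and attends, and that every current NRT user fails cotinine. The validated rates are then 12.0 × (1 − uE) and 6.0 × (1 − uC). The documents give neither share, so a range is shown.

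| uE | uC | Experimental | Control | Difference (points) | Risk ratio | Validated total |
|---|---|---|---|---|---|---|
| 0% | 0% | 12.0% | 6.0% | 6.0 | 2.00 | 108 |
| 5% | 5% | 11.4% | 5.7% | 5.7 | 2.00 | 102.6 |
| 10% | 10% | 10.8% | 5.4% | 5.4 | 2.00 | 97.2 |
| 20% | 20% | 9.6% | 4.8% | 4.8 | 2.00 | 86.4 |
| 30% | 30% | 8.4% | 4.2% | 4.2 | 2.00 | 75.6 |
| 10% | 5% | 10.8% | 5.7% | 5.1 | 1.89 | 98.3 |
| 5% | 10% | 11.4% | 5.4% | 6.0 | 2.11 | 101.5 |

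With equal shares, the factor (1 − u) cancels from the ratio and the difference is 6.0 × (1 − u). With unequal shares, the ratio moves down or up according to which arm has more continuing NRT users.

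**Step 4: is NRT status known at 6 months?** Section 5 names 1 and 3 months for NRT use, but its general sentence on self-reported outcomes also covers 6 months. The text supports either reading.

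**The case against.** The strongest reply is that no consequence has been shown. The step from NRT to raised cotinine comes from general pharmacology, not from the documents. The trial supplies one week of NRT, finished long before the 6-month test. The documents do not say how long clinic NRT lasts or who still uses it, so the true share could be zero. All of this stands, and it limits the size of the point. It does not remove the gap, because the rule as written makes no allowance for any such participant and the pharmacology is uncontroversial.

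A second reply is that requiring both markers is a defensible conservative choice. The trial admits users of any tobacco product, CO detects only recent smoking of combusted tobacco, and Section 15.1.1.5 anticipates people using cigarettes and NRT together. This also stands, and it is why the definition should be kept.

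A third is that self-reported 7-day and 4-week abstinence at 6 months are separate outcomes that do not depend on cotinine, and that CO and cotinine are separate measurements from which cotinine-only failures can be counted. Both are correct. The plan nevertheless does not undertake to report that count.

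Two stronger readings are tempting. A reader might infer from the pilot's NRT use of 34% versus 2% (Section 7) that the rule penalises the experimental arm. Those figures are from 3 months, and the pilot "had not referred the smokers to SC clinics", whereas here both arms are directed to clinic NRT. They give neither the 6-month share nor its direction. A reader might also infer that NRT use is not collected at 6 months, so that the problem could never be seen in the data. Section 5 is ambiguous on this and does not establish it.

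**Conclusion.** The point holds as a minor one. A tobacco-free participant regularly using NRT at the 6-month test would be expected to be classed as not validated, so validated abstinence could be understated. In the illustration, equal NRT shares up to 30% reduce the difference from 6.0 to as little as 4.2 points and leave the risk ratio at 2.00; shares of 10% versus 5%, and the reverse, give ratios of 1.89 and 2.11.

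These figures rest on assumed NRT shares, the pooled 30% target applied to service users in each arm, no abstinence among other participants, truthful self-report, full attendance at testing, and cotinine failure in every NRT user. They show scale and are not estimates. The documents support no direction of bias between arms. One secondary outcome is affected; the two primary outcomes, the sample size and self-reported abstinence are not.

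**What to change.** Keep the two-marker definition as the outcome. In every case, report by arm the number failing on cotinine only (CO < 4 ppm, cotinine ≥ 10 ng/ml).

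Add one sensitivity analysis. Self-reported quitters who report current NRT use, and whose tobacco use was conventional cigarettes only, are validated on CO < 4 ppm alone; all others need both tests. Report by arm the number validated on CO alone.

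How this is done depends on timing. The document date and the proposed completion date (Section 6) are both 30 June 2020, so data collection may already be closed.

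- (a) Follow-up still open: state in Section 5 that current NRT use and tobacco product type are recorded at the 6-month validation, and pre-specify the analysis.
- (b) Data collection complete and these items recorded: run the same analysis, labelled as added after data collection.
- (c) Data collection complete and these items not recorded: report CO-only and two-marker results by arm, with the same label.

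The cost is a few sentences and a few extra table entries per arm, with at most two added questions under (a) and no new test. The downside is leniency: CO misses tobacco that is not burned and smoking that is not recent, and the CO-only route in (a) and (b) depends on self-reported NRT use after randomisation, so it may be too generous, possibly more so in one arm. For that reason it should remain a sensitivity analysis.

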15.2.3 Participants who do not make an intake appointment

The participants will receive motivational messages from the research assistant around one week after baseline to encourage them to quit and enroll in one of the SC clinics.

16. Indicators and targets

Our targets will be as follows:

1. Train 40 tertiary students to be SCAs
2. Deliver brief SC advice to 2,400 smokers (1,200 in the experimental and 1,200 in the control group)

Experimental group

3. Provide NRT sample to 720 smokers (60% of all the approached smokers), who also consent to the follow-up
4. Motivate 288 smokers (40%) to use any SC services
5. Motivate 144 smokers (20%) to attempt quitting (intended abstinence for at least 24 hours).

Control group

6. 360 smokers (30% of all the approached smokers) will consent to the follow-up.
7. Motivate 72 smokers (20%) to use any SC services
8. Motivate 28 smokers (8%) smokers to attempt quitting

Both groups

9. 108 smokers report abstinence (for the past 7 days) at 6-month follow-up (30% of all

the 360 smokers who use any SC services)

17. Sample size determination

To detect a significant difference of the rate of quit attempt (20% versus 8%) with normal test and a power of 95% and 5% significance level, we need 485 subjects in the RCT (allocation ratio 2:1; 323 vs 162). Based on the method of Eldridge et al. (2006) [26], conservatively assuming that we could recruit 8 participants per session on average and the intra-cluster correlation coefficient was 0.1, the design effect is estimated to be 1.7. Thus, the minimum sample size required for the trial is 825 (=1.7 X 485) participants and 60 sessions in total. With the similar calculation, the required sample size for detecting a significant difference in the proportion of using any SC service is 421. Therefore, our targeted sample size is sufficient to answer the research question.

18. Data analyses

To assess the change of knowledge, attitude and practice of SC due to the participation of the SCA workshop, all the outcomes will be tested by McNemar's test (binary outcomes) and pair-sample t-test (continuous outcomes).

To assess the effect of NRT sampling to the recruitment outcomes, the number of smokers who accept the brief advice or consent for the trial in each promotion session will be the outcome variables of Poisson regression model, with group allocation as the predictor, and total number of approached smokers in that promotion session as the offset variable.

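### Smokers join after the arm is known, at targets of 60% versus 30% of those approached, and the primary quitting analysis has neither baseline adjustment nor a check for selection

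*Combined protocol and SAP*

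**What the plan says.** Section 12 randomises sessions, not people. Section 13 states: "All recruitment staff will know the group allocation before each promotion session, so no group concealment can be done". Section 14 adds that participants are not blinded. The pragmatic provisions at the end of section 11 allow that "the intervention components and filling in of baseline questionnaire may be carried out prior to seeking the consent from the participant".

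Section 8 expects the offer to change who takes part ("Because smokers who receive NRT sampling will be more likely to participate in the study, the experimental sessions will then recruit more smokers") and gives this as the reason for the 2:1 ratio. Section 16 sets the targets, with 1,200 smokers advised per arm:

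- Experimental: "Provide NRT sample to 720 smokers (60% of all the approached smokers), who also consent to the follow-up".
- Control: "360 smokers (30% of all the approached smokers) will consent to the follow-up".

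The one design step aimed at balance is in section 8: "To increase comparability between the two groups, the promotion sessions of one hotspot will be randomly allocated to either group". Section 14 also blinds outcome assessors and analysts.

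Section 18 compares both primary quitting outcomes by GEE. It names no covariates, no weighting and no sensitivity analysis for selection. Differential recruitment appears only as an outcome in its own right, in a Poisson model with the "total number of approached smokers in that promotion session as the offset variable".

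**The concern.** Randomising sessions makes the smokers who pass by comparable. It does not make those who agree to join comparable when the offer that drives joining differs by arm and is known beforehand. Section 15 follows up consenters only, so the primary comparison is between two differently selected groups. GEE allows for correlation within sessions but does nothing about who entered.

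The protocol's own background makes outcome-related selection plausible. Section 7 reports that about 72% of smokers recruited earlier at hotspots intended to quit, and that most of those approached declined follow-up, being probably either self-quitters or hardcore smokers. Doubling the joining rate in one arm could therefore change the mix.

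The direction is not known. Free NRT may draw in people keener to try quitting, or people who mainly want the sample. The first would exaggerate the effect and the second would hide it. A larger trial would only estimate the wrong quantity more precisely.

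**Working it through.** **The plan's own figures.** For 20% versus 8%, two-sided 5%, 95% power, 2:1 and pooled variance, the control arm needs 161.4. This gives 162 + 323 = 485, as stated in section 17. The design effect is 1 + (8 − 1) × 0.1 = 1.7, and 1.7 × 485 = 824.5, stated as 825. Entry targets are 720/1,200 = 60% and 360/1,200 = 30%. All reproduce.

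**Share of the experimental arm without a counterpart.** Assume the offer never deters anyone who would have joined a control session. The excess fraction is q = (0.60 − 0.30)/0.60 = 0.50, or 360 of 720.

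**False benefit when there is no effect (quit attempts).** The documents give no attempt rate for the extra recruits, so x is an assumption. Would-be joiners attempt at 8% in both arms, so the experimental arm shows p₁ = (8% + x)/2 against p₀ = 8%. The chance of a significant benefit is Φ[(p₁ − p₀ − 1.96·s₀)/s₁], where s₀ and s₁ are the pooled and unpooled standard errors at sizes 720/DE and 360/DE. Worked case for DE = 1.7, x = 16%: p₁ = 12%, s₀ = 0.0260, s₁ = 0.0244, and (0.04 − 0.0509)/0.0244 = −0.447, which gives 32.7%.

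| x | p₁ | DE 1.7 | DE 2.7 |
|---|---|---|---|
| 8% | 8% | 2.5% | 2.5% |
| 12% | 10% | 11.8% | 8.7% |
| 16% | 12% | 32.7% | 21.6% |

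The 2.7 is not the plan's figure. It takes the 1,080 target over the 60 sessions in section 17, so 18 per session and 1 + 17 × 0.1 = 2.7. Section 17's own numbers do not agree on session size (825/8 = 103 sessions, not 60), so 2.7 is only a sensitivity case.

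With no effect at all, the 20% versus 8% used to size the trial would appear if x = 2 × 20% − 8% = 32%.

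**Bias in the other direction.** If would-be joiners reach 20% with NRT but extra recruits only 8%, the experimental arm shows 14%. Power falls from 98.6% to 60.0% at DE 1.7, and from 90.1% to 40.6% at DE 2.7.

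**Trimming bounds at the targets**, for those who would join under either offer:

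- Quit attempts: lower max(0, (0.20 − 0.50)/0.50) − 0.08 = −8 points; upper 0.20/0.50 − 0.08 = +32 points.
- Service use (40% versus 20%): lower 0 − 0.20 = −20 points; upper 0.40/0.50 − 0.20 = +60 points.

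Before sampling error, the lower bound exceeds zero only if q < 0.12/0.92 = 0.130 for quit attempts, or q < 0.20/0.80 = 0.25 for service use. With 60% experimental entry, control entry must exceed 52.2% or 45% respectively.

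**Tipping point per approached smoker (quit attempts).** Let uₑ and u_c be the attempt rates among unfollowed smokers in the experimental and control arms. The arms are equal when 0.6 × 0.20 + 0.4·uₑ = 0.3 × 0.08 + 0.7·u_c. For uₑ = 0%, 4% and 8%, u_c = 13.7%, 16.0% and 18.3%. These are exactly the control rates implied by pure selection with x = 32%, since (0.3 × 0.32 + 0.4·uₑ)/0.7 gives the same values. Forcing one common unfollowed rate on both arms would hide that scenario.

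**The case against.** **Shared screening.** Section 10 has ambassadors raise NRT only with smokers already interested in cessation services. Section 11 applies the same procedures to control sessions apart from the sample and instruction card. Eligibility, advice script and nurse counselling are also common. This could narrow motivational differences among entrants and keep x closer to 8%. It stands as a mitigating factor, but it does not remove the gap that the plan itself targets.

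**Targets are not observations.** If control entry were 45% rather than 30%, the false-benefit chance at x = 12% would be about 7%; at 50% it would be about 5%. The 60% also counts only consenters who receive a sample, while section 15.1 provides for experimental participants without one. Section 16 applies the word approached to the 1,200 given advice, whereas section 5 separates the two groups. These points make the size uncertain in both directions. The pilot's 81.3% participation is no reassurance, because that trial randomised individuals and this one targets 30% in control sessions.

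**The remedy is partial.** Adjustment handles only measured differences, the questionnaire's content is not listed, and motivation items are excluded because they may follow intervention. Wide bounds will not settle the question. This is correct, but wide bounds would show how far the result depends on untested assumptions, which the present plan leaves hidden.

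**Higher recruitment is an intended effect.** It is, and it has its own outcome and model. That does not make the quitting comparison unbiased, and section 4 sets out to evaluate the effectiveness of NRT sampling on quitting.

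**Conclusion.** The concern holds and must be fixed. Followed exactly, the plan could attribute to NRT sampling a difference that comes from who enrolled, or miss a real effect for the same reason. Within-hotspot allocation and blinded assessment address place and measurement, not consent. The Poisson model measures the recruitment gap but does not carry it into the quitting comparison.

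At the plan's targets the distortion is material: moderate assumed differences in the extra recruits produce several times the nominal false-benefit rate or a large loss of power, and the bounds for both primary outcomes include no effect. The size rests on the 60% and 30% targets, the assumed rates for extra recruits and, for the bounds, on the offer deterring nobody. The direction cannot be determined from the documents. The absence of any safeguard in section 18 does not depend on these assumptions.

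**What to change.** Amend section 18 before the arms are compared; anything added later should be labelled post hoc.

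1. Make the primary GEE for both quitting outcomes adjusted for a short prespecified list of baseline variables that the intervention cannot change: for example age, daily cigarette consumption and factual smoking history, plus sex if recorded. Check each against the on-site form. Leave out attitude items, which may be recorded after intervention components. Use exhaled CO only with a stated rule for those not measured, since section 9 limits it to users of conventional cigarettes. Report the unadjusted GEE as supportive and tabulate baseline characteristics by arm.
2. Add a selection sensitivity analysis that does not assume equal rates among unfollowed smokers in the two arms: either trimming bounds with intervals resampled by session, or a tipping-point analysis with a separate rate per arm. Define the recruitment proportion as RCT participants over approached smokers, not the section 5 process outcome, which also counts clinic-only enrolees.
3. State that the conclusion applies to recruited smokers and may reflect residual selection if the bounds include no effect.

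The cost is SAP wording and modest analysis time. No new data are needed, because approach and consent counts per session are already recorded. The downsides should be stated: adjustment removes measured selection only, approach counts are made by staff who know the arm, and the bounds may be wide.
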